- After the completion of the in-clinic observation study, the Data Monitoring Committee (DMC) will convene to review the safety data.
- DMC will review in clinic data from subjects in the 5-6 year age group (N=8), in order to assess that it is safe for 5-6 year olds to perform Cohort A or Cohort C study procedures.
- DMC will review in-clinic data from both the 2-4 year age group (N=8) and the 5-6 year age group (N=8) in order to assess that it is safe for 2-4 year olds to perform Cohort A and Cohort C study procedures.
- While waiting for approval by the DMC after completing the in clinic observational study, subjects will use the AHCL system at home in Manual Mode. If subject was using 670G with Auto Mode at Screening, the subject may use Auto Mode with the Auto Correction feature off (i.e., not enabled).
- The observational study may be divided into two different weekends based on investigator discretion to provide improved flexibility for parents and child.
- Friday to Sunday x 1
- Saturday to Sunday x 1
- When not in clinic to perform the observational study, subjects should be in Manual Mode. If subject was using 670G with Auto Mode at Screening, the subject may use Auto Mode with the Auto Correction feature off (i.e., not enabled).
- Upon receiving approval to proceed from the DMC, subjects may return to using Auto Mode.

Visit Schedule for Cohort A: Device Settings Adaptation (Digital Twin) – Challenges #1 and #2

Visit Schedule for Cohort C: Meal Prediction

6. Determination of Sample Size

A total of up to 200 subjects will be enrolled at up to 15 investigational centers across the US in order to have up to 150 subjects who complete the study.

It is expected that at least N=12-18 subjects will participate in each phase during Feasibility 2.

Given that this study is not statistically powered, no sample size calculation was performed. Up to 200 subjects will be enrolled to demonstrate a feasibility of an outpatient study using the Medtronic insulin pump system.

7. Statistical Methods

7.1 Study Subjects

7.1.1 Disposition of Subjects

The number of subjects enrolled in the study will be presented. The reasons for subject discontinuation prior to study completion will be summarized.

7.1.2 Clinical Investigation Plan (CIP) Deviations

All protocol deviations will be presented in the listings.

7.1.3 Analysis Sets

All enrolled subjects who have participated in the study will be included in the efficacy analysis population per each phase analysis. All enrolled subjects will be included in the safety analysis population.

7.2 General Methodology

No statistically powered analyses or hypothesis testing will be performed. Summary and descriptive statistics will be performed.

7.3 Center Pooling

Data will be pooled for analysis.

7.4 Handling of Missing, Unused, and Spurious Data and Dropouts

All available data will be included in the data listings and tabulations. No imputation will be applied for the missing data.

7.5 Adjustments for Multiple Comparisons

Not applicable.

7.6 Demographic and Other Baseline Characteristics

Subject characteristics, including age, gender, race, ethnicity, height, weight, and BMI will be summarized by descriptive statistics (mean, standard deviation, minimum, median, and maximum) for continuous variables and by counts and percentages for categorical variables.

7.7 Treatment Characteristics

Not applicable.

7.8 Interim Analyses

Not applicable.

7.9 Evaluation of Objectives

Descriptive Endpoints

There are no statistically powered endpoints or hypothesis testing but there are descriptive endpoints.

7.9.1 Effectiveness Endpoints

- Percentage of time in target: SG <70 mg/dL, 70-180 mg/dL and > 180 mg/dL

Analyses in detail, if applicable:

- Overall percentage of time in severe hypoglycemia: SG <54 mg/dL
- Overall percentage of time in severe hyperglycemia: SG >250 mg/dL
- Overall mean SG and standard deviation of SG
- Postprandial analysis, up to 5h post-meal period
 - Postprandial SG mean, peak SG, SG nadir (post peak), AUC >180 mg/dL, and time in target (SG <70 mg/dL, SG <54 mg/dL, 70-180 mg/dL and > 180 mg/dL)

Descriptive subgroup analysis for the above analyses will be performed in the following cohorts:

Cohort A: Recommended Settings

Cohort C: Meal Prediction

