#### **Digital Twin Challenge #1: Alternating Between Auto Mode & Manual Mode**

**Purpose:** The purpose of this challenge is to observe subject safety when subjects frequently exit Auto Mode and transition back and forth between Auto Mode and Manual Mode. The purpose of this data collection is also to assist in the development of the Digital twin algorithm.

**Rationale:** Patients sometimes intentionally switch from Auto Mode to Manual Mode for brief periods of time depending on their circumstances.

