The table below shows an example of a transition schedule between Auto Mode and Manual Mode; different variations will be provided by the Sponsor to the investigational center. The transitions between Auto Mode and Manual Mode should occur between 7am and 12 Noon.

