**Table 2. Example of Manual mode Transitions during the study period - Digital Twin Challenge #1**

Week	Day 1	Day 2	Day 3	Day 4	Day 5	Day 6	Day 7
1	Manual Mode	Auto Mode	Auto Mode	Auto Mode	Auto Mode	Auto Mode	Auto Mode
2	Auto Mode	Auto Mode	Manual Mode	Auto Mode	Auto Mode	Auto Mode	Auto Mode
3	Auto Mode	Auto Mode	Auto Mode	Auto Mode	Manual Mode	Auto Mode	Auto Mode

Week	Day 1	Day 2	Day 3	Day 4	Day 5	Day 6	Day 7
4	Auto Mode	Manual Mode	Auto Mode	Auto Mode	Auto Mode	Auto Mode	Auto Mode
5	Auto Mode	Auto Mode	Auto Mode	Manual Mode	Auto Mode	Auto Mode	Auto Mode

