## **9.9. Deviation Handling**

A deviation is any instance(s) of failure to follow, intentionally or unintentionally, the requirements of the CIP. It is expected that the investigator will conduct this clinical trial in compliance with the CIP and all applicable regulations governing the conduct of clinical research involving human subjects. Failure to do so could result in one or all of the following:

- Investigational center disqualification
- Notification to the regulatory authorities/IRB depending on the severity of the deviation and reporting requirements

The investigator should not implement any deviation from, or changes to, the CIP without agreement by the sponsor and prior review and documented approval/favorable opinion from the IRB, except where

necessary to eliminate an immediate hazard(s) to trial subjects or when the change does not affect the scientific soundness of the plan or the rights, safety, and welfare of the subjects.

The following are deviations related to study procedures:

- If subjects do not follow the fingerstick recommendations, no study deviation will be given unless the site staff did not train the subject on SMBG study procedures.
- If subjects do not upload devices perfectly, no study deviation will be given unless the site staff did not train the subject on upload procedures.
- As it can occur that subjects do not follow study instructions perfectly, such as uploading their pumps, changing between Auto Mode and Manual Mode, no study deviation will be given unless site staff did not provide sufficient instructions to subjects regarding study requirements.
- If subject does not collect enough blinded CGM data during the run-in period, no study deviation will be given as long as subject made effort to wear the blinded CGM.

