## 9.13. Success Criteria for Feasibility 2 (Digital Twin and Meal Prediction)

The following criteria will be used to evaluate success of the Feasibility 2:

No occurrence of severe hypoglycemia or DKA due to device algorithm during the feasibility studies

1. Average time with SG below 70 mg/dL of 47 minutes or less (i.e.  $\leq 3.3\%$ ) as in CER294DOC

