Following the run-in period, subjects will participate in a study period lasting approximately 5-6 weeks. For the duration of the study period, subjects will be asked to switch back and forth between Auto Mode and Manual Mode, according to a schedule that will be provided to each site by the Sponsor. Subjects will be instructed to upload the pump and meter at specific time points during the study period. Device settings recommendations will be provided during this study period. Investigators should make every attempt to follow these recommendations, except if they do not agree with the device settings recommendations, based on safety concerns. Investigators may adjust device settings based on safety.

Device Setting changes

At the start of the study period, insulin delivery settings based on data collected during the run-in period will be made available to the investigator.

- If the investigator agrees with the new settings, they will be programmed into a subject's study pump.
- If the investigator does not agree with the recommendations, they may be implemented gradually over a period of time, e.g. 1-2 weeks.
- If the investigator does not agree with the recommendations and does not wish to implement them gradually, details about the disagreement will be noted on the applicable CRF.

After approximately 2 weeks of the study period, following a pump upload by subjects at home, new device settings will be made available.

- If the investigator agrees with the new settings, they will be programmed into a subject's study pump.
- If the investigator does not agree with the recommendations, the investigator will enter details about the disagreement on the applicable CRF.

After approximately 3 weeks of the study period, following a pump upload by subjects at home, new device settings will be made available.

- If the investigator agrees with the new settings, they will be programmed into a subject's study pump.
- If the investigator does not agree with the recommendations, the investigator will enter details about the disagreement on the applicable CRF.

After approximately 4 weeks of the study period, following a pump upload by subjects at home, new device settings will be made available.

- If the investigator agrees with the new settings, they will be programmed into a subject's study pump.
- If the investigator does not agree with the recommendations, the investigator will enter details about the disagreement on the applicable CRF.

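### The planned sensor glucose summaries for Challenge #1 are not split by pump mode or timed to mode switches, so a rise in non-severe hypoglycemia on Manual Mode days would be heavily diluted

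*SAP*

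**What the plan says.** Protocol section 5 gives the purpose of Challenge #1 as to "observe subject safety when subjects frequently exit Auto Mode and transition back and forth between Auto Mode and Manual Mode". A second stated purpose is to support development of the Digital Twin algorithm.

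Table 2 is headed "Example of Manual mode Transitions during the study period - Digital Twin Challenge #1" and shows one Manual Mode day in each of five weeks. The text before it says that "different variations will be provided by the Sponsor to the investigational center", and adds: "The transitions between Auto Mode and Manual Mode should occur between 7am and 12 Noon". SAP section 5 says that "subjects will participate in a study period lasting approximately 5-6 weeks".

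SAP 7.9.1 lists percentage of time with SG below 70, at 70-180 and above 180 mg/dL. Where applicable, it adds overall time below 54 and above 250 mg/dL, overall mean and SD of SG, and a postprandial analysis. It continues: "Descriptive subgroup analysis for the above analyses will be performed in the following cohorts", and names Cohort A and Cohort C. Protocol 14.4.3 promises a summary in each phase. No pump mode and no time window is attached to any of these metrics.

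Protocol 9.13 sets a Feasibility 2 success criterion of "Average time with SG below 70 mg/dL of 47 minutes or less", also without a mode split. Protocol 9.9 says, of subjects who do not follow instructions such as "changing between Auto Mode and Manual Mode, no study deviation will be given unless site staff did not provide sufficient instructions".

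**The concern.** The time that bears on the question of Challenge #1 is the Manual Mode time and the hours after each return to Auto Mode. The planned SG metrics do not isolate either. They blend that time with ordinary Auto Mode time, which is most of the example schedule.

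Protocol 10.1 (Table 6) itself lists low or high glucose related to entering or leaving Auto Mode as a risk. Protocol 11.3 does not expect hypoglycemia short of the severe definition to be reported as an adverse event. The SG metrics are therefore the main planned view of non-severe hypoglycemia in this challenge.

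A reassuring mean could have two explanations: switching was well tolerated, or subjects seldom switched. The planned tables would not separate them. This matters beyond the final report. Under Protocol 12.2, children aged 2-13 enter a phase only after 10 older subjects have completed the corresponding phase and the DMC has reviewed safety data. No by-mode summary is specified for that review.

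**Working it through.** **Inputs.**
- Example schedule: 5 Manual Mode days in 35 (Table 2).
- Criterion: 47 min/day below 70 mg/dL, also stated as 3.3% or less (Protocol 9.13). It applies to Feasibility 2 and is used here only as a yardstick.
- Time below 70 mg/dL on Auto Mode days: the documents give no value. Assumed 2.0%, 2.5% and 3.0%, which are 28.8, 36.0 and 43.2 min/day.

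**The plan's own figure.** 47/1440 = 3.26%, which rounds to the stated 3.3%.

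**Dilution.** Manual Mode share w = 5/35 = 1/7 = 14.3%; Auto Mode share = 30/35 = 85.7%. Overall mean = w × Manual + (1 − w) × Auto. A 5-point rise on Manual Mode days shifts the overall mean by 5 × 1/7 = 0.71 points.

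**Largest Manual Mode value that still meets 47 min/day.** Manual = 7 × 47 − 6 × Auto, in min/day:

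| Auto Mode days (assumed) | Manual Mode limit, min/day | Manual Mode limit, % of time | Ratio to Auto |
|---|---|---|---|
| 2.0% | 329 − 172.8 = 156 | 10.85% | 5.4 |
| 2.5% | 329 − 216.0 = 113 | 7.85% | 3.1 |
| 3.0% | 329 − 259.2 = 70 | 4.85% | 1.6 |

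For example, with Auto Mode days at 2.5%, a tripling to 7.5% on Manual Mode days gives (30 × 2.5 + 5 × 7.5)/35 = 3.21%, which still meets the criterion.

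**How far the 1/7 share can move.**
- Switches between 7am and noon make a Manual Mode day last 19 to 29 h. The share is then 5 × 19/840 = 11.3% to 5 × 29/840 = 17.3%.
- Visit 11 to Visit 18 is nominally 7 + 8 + 8 + 8 + 7 = 38 days: 5/38 = 13.2%.
- If 30 run-in days in Auto Mode were included: 5/65 = 7.7%.
- If Challenges #1 and #2 were pooled in equal numbers under Cohort A: 5/70 = 7.1%. The per-phase summary in Protocol 14.4.3 would avoid this.
- A sponsor schedule with more Manual Mode days would raise the share. The documents set no number.

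**The case against.** The strongest reply is that the designated safety endpoints are events. SAP 7.10 counts severe hypoglycemia, DKA and all adverse events whatever the mode, and averaging does not dilute a count. Under Protocol 12.1 the CEC reviews each severe glycemic event and may look at pump and sensor data. The SG percentages are labelled effectiveness endpoints, the study is descriptive, and its objective is data collection. All of this stands. It limits the point to hypoglycemia below the Protocol 11.2 definition of severe. It does not supply a by-mode SG summary, and none is planned anywhere else.

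A reader might go further in four ways that the documents do not support.
- *The plan averages all metrics over the whole study period.* SAP 7.9.1 attaches the word overall only to time below 54, time above 250, and mean and SD. The main endpoint line names no window. The supportable statement is that window and mode are unspecified.
- *Six-sevenths Auto Mode is the design.* It is the share in an example, and other schedules may be supplied.
- *Non-switching leaves no trace.* Protocol 9.9 only waives the deviation when instructions were sufficient. Table 6 says that data from both modes feed the Digital Twin, and sites review uploads throughout, so mode should be derivable. The gap is that no table is planned.
- *Phases 1 and 2 cannot answer their question.* They can still answer it for severe events, and they serve algorithm development as well.

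**Conclusion.** The point holds as a mismatch between the purpose of Challenge #1 and its planned SG summaries. No SG metric is reported by pump mode or around a switch, and no summary shows how much switching occurred.

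Under the example schedule the dilution is about sevenfold. The room it leaves depends strongly on the Auto Mode level. At an assumed 2.0%, Manual Mode days could reach more than five times that level before the 47 min/day average is exceeded. At 3.0% the ratio is 1.6, so far less could go unseen. These figures rest on 5 Manual Mode days in 35, full adherence, no unplanned exits from Auto Mode, and the assumed Auto Mode values.

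No error rate or sample size is affected, because nothing is tested or powered. Description is what the study delivers, however, so the plan should describe the time that the challenge is about.

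**What to change.** In SAP 7.9.1, for study-period data from Phases 1 and 2, add within-subject descriptive summaries of the same SG metrics for three kinds of time:
1. Manual Mode.
2. A prespecified window after each return to Auto Mode. The documents do not fix a length; 24 h is one option.
3. All remaining Auto Mode time.

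Classify time by the mode that the pump recorded, not by the schedule, because switch times vary and subjects may not switch. Report completed switches and Manual Mode hours per subject, and the hours and subjects contributing to each summary. State that run-in data and Challenge #2 are kept separate. Make the same tables available for the DMC review that precedes Phase 2.

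The cost is a paragraph of SAP text and a few tables from pump data already uploaded to CareLink. No visit, procedure or device setting changes. The downside is precision. At one Manual Mode day per week and the expected 12-18 subjects per phase, the Manual Mode summaries rest on about 5 × 12 = 60 to 5 × 18 = 90 subject-days, 5 per subject. They will be noisy and should be presented with their spread.

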7.9.2 ABL90

Descriptive statistics will be performed for ABL-90 glucose value vs. MBG and ABL-90 glucose value vs. SG after pairing. Metrics included 20/20% agreement (± 20 mg/dL when MBG/SG less than ($<$) 80 mg/dL), bias and MARD.

7.10 Safety Evaluation

- Severe glycemic events: (i.e., severe hypoglycemia, DKA)
- Collection of ALL adverse events (i.e. Summary of device related adverse events)

7.11 Health Outcomes Analyses

Not applicable.

7.12 Changes to Planned Analysis

Not applicable.

8. Validation Requirements

Level I or Level II validation are required for analysis output. Level I requires that the peer reviewer independently programs output and then compares the output with that generated by the original Statistical Programmer. Level II requires that the peer reviewer reviews the code; where appropriate, performs manual calculations or simple programming checks to verify the output.

9. References

Not Applicable.
